#### 4.3 Discontinuation of Subjects

A subject may withdraw from the study, or the parent/LAR may withdraw the subject from the study, at any time for any reason without prejudice to their future medical care by the physician or at the institution. The investigator or sponsor may withdraw the subject at any time (eg, in the interest of subject safety). The investigator is encouraged to discuss withdrawal of a subject from investigational product with the medical monitor when possible.

If investigational product is discontinued, regardless of the reason, the evaluations listed for Visit 16/early termination (ET) are to be performed as completely as possible. Whenever possible, all discontinued subjects should also undergo the protocol-specified follow-up. Comments (spontaneous or elicited) or complaints made by the subject must be recorded in the

source documents. The reason for termination, date of stopping investigational product, and the total amount of investigational product taken must also be recorded in the source documents and the most clinically relevant reason should be entered on the CRF.

Subjects who discontinue will not be replaced.

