#### 6.2.3 Dosing

Dosing should begin at 7:00 AM ( $\pm 2$  hours) on the morning after the baseline visit (Visit 2). The parent/LAR responsible for dosing will be instructed to dispense 1 capsule to the subject daily in the morning throughout the study, at approximately the same time each day. The same parent/LAR should be available daily to dispense the dose of investigational product for the study duration.

SHP465 may be administered in 1 of the following ways:

- Swallow SHP465 capsule whole, or
- Open capsule and sprinkle the entire contents on applesauce

The sprinkled applesauce should be consumed immediately; it should not be stored. Subjects should take the sprinkled applesauce in its entirety without chewing. The dose of a single capsule should not be divided. The empty capsule shells should be discarded.

Subjects will be treated with SHP465 at 6.25 mg.

The investigator will categorize subject response into 1 of the following 3 conditions, along with the associated actions:

- **Intolerable response** (ie, subject experiences intolerable side effects): If this lower dose also produces an intolerable effect, the subject should be discontinued from the study.
- **Ineffective response** (ie, subject has not achieved at least a 30% reduction in ADHD-RS-5 Child, Home Version total score from the baseline visit [Visit 2] and a CGI-I score of 1 or 2).
- **Acceptable response** (ie, subject has achieved at least a 30% reduction in ADHD-RS-5 Child, Home Version total score from the baseline visit [Visit 2] and a CGI-I score of 1 or 2 with tolerable side effects): This response suggests that an optimal dose has been achieved and the subject should maintain this dose for the remainder of the study.

If the subject experiences unacceptable tolerability, in the opinion of the clinician, the subject will be discontinued.

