11. SAFETY ANALYSES

Safety data will be analyzed for the Safety Set by treatment group of the antecedent studies, current treatment (SHP465) for each enrollment type, and overall. Safety endpoints include the occurrence of TEAEs, vital signs (systolic and diastolic blood pressure, and pulse), height, weight, body mass index (BMI); clinical laboratory and ECG results, C-SSRS, and sleep questionnaires (PSQ and CSHQ). For each safety endpoint, the last value collected before the first dose of investigational product in this study will be used as baseline for all analyses of that safety endpoint. Except for adverse event data, only post-baseline assessments from Visit 2 (Week 0) up to Visit 16 (Month 12) that were collected on or 2 days after the last dose of investigational product will be analyzed. A Final on-Treatment Assessment (FoTA) will be defined as the last valid assessment obtained after Baseline and whilst on investigational product (on or before 2 days after the last dose date).

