11.5.1 Columbia-Suicide Severity Rating Scale (C-SSRS)

The C-SSRS is a semi-structured interview that captures the occurrence, severity, and frequency of suicide-related thoughts and behaviors during the assessment period. The interview includes definitions and suggested questions to solicit the type of information needed to determine if a suicide-related thought or behavior occurred.

The C-SSRS contains two required items pertaining to suicidal ideation, four required items pertaining to suicidal behavior, and one required item pertaining to non-suicidal self-injurious behavior. There are eight additional suicidal ideation items and two additional suicidal behavior items which are completed in cases of positive responses for other items, as well as two items for suicide and suicide behavior present during the interview. Most items are rated on a dichotomous scale (yes or no) or 3- or 5-point Likert scale. In addition, the total number of attempts (including interrupted and aborted attempts) is recorded. In the event of a positive categorical response the interviewer can provide text or narrative that further describes the thought or behavior.

Two versions of C-SSRS, the "Baseline" version and the "Since Last Visit" version, will be used in this study. For subjects in Group A, the "Since Last Visit" version will be completed at all study visits. The scale will be compared with the "Baseline" version from the antecedent study. For subjects in Group B, the "Baseline" version will be administered at the Screening Visit (Visit 1) and the "Since Last Visit" version will be completed for all subjects at all study visits after the Screening Visit (Visit 1).

Positive results from the C-SSRS data will be descriptively summarized for overall during the study and by visit.

A listing of the C-SSRS data will be provided for subjects with a positive response.

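### The SAP's 2-day cut after last dose works by collection date, so a late final C-SSRS 'Since Last Visit' form is left out of the C-SSRS summaries even when most of its recall period is on drug

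*SAP*

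**What the plan says.** SAP 11 lists the C-SSRS among the safety endpoints, exempts only adverse event data, and analyzes "only post-baseline assessments from Visit 2 (Week 0) up to Visit 16 (Month 12) that were collected on or 2 days after the last dose". Taken literally, the last clause admits only two collection days. The definition of the Final on-Treatment Assessment (FoTA) in the same section sets the limit at no later than 2 days after the last dose date, and that is clearly what is meant.

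For baseline, SAP 11 says that "the last value collected before the first dose of investigational product in this study will be used as baseline for all analyses".

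SAP 11.5.1 describes an interview about events during an assessment period. The 'Since Last Visit' version is used at all visits in Group A and at all visits after screening in Group B. On analysis it says: "Positive results from the C-SSRS data will be descriptively summarized for overall during the study and by visit". It adds a listing of subjects with a positive response and states no date window.

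Protocol 4.3 requires that, once drug is stopped for any reason, "the evaluations listed for Visit 16/early termination (ET) are to be performed as completely as possible". It gives no limit on how long after the last dose this may happen. SAP 18.3 assigns each ET assessment to the next nominal visit, so ET data are meant to be tabulated.

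**The concern.** A cut by collection date suits point measurements such as blood pressure, pulse or an ECG: a reading taken several days after the last dose says little about the on-drug state. A 'Since Last Visit' form is different. It describes the time back to the previous visit, and at an ET visit much of that time is usually on drug. Dating the form by the day it was completed discards the on-drug period along with the few days off drug. SAP 11.1 treats comparable information differently: a treatment-emergent adverse event (TEAE) is assigned by its own date, up to 3 days after the last dose.

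C-SSRS responses are named in the primary safety objective (Protocol 2.2.1, SAP 3.1). If a positive response appears only on a late final form, the summary counts that child as 0 instead of 1. Late final forms are foreseeable. Protocol 4.3.3 asks families lost to follow-up to return for final safety evaluations, and SAP 1 records that the sponsor ended the study on 14 Dec 2018, so early ends may be common.

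**Working it through.** The plan gives no figure to reproduce here. The check is day counting on the visit schedule.

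**Inputs.** Nominal visit days 0, 7, 14, 30, then every 30 days to 360 (Protocol Tables 1 and 2). Cut: keep a form if collection day minus last-dose day is at most 2 (SAP 11, FoTA reading). The ET delay and the distribution of stop days are not in the documents and are assumed below.

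**Worked record.** Previous visit Day 60, last dose Day 80, ET visit Day 84.
- Delay: 84 − 80 = 4 days, more than 2, so the form is excluded.
- Recall period: Days 61 to 84, which is 24 days.
- On drug within it: Days 61 to 80, which is 20 days, or 20/24 = 83%.

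**Final form collected at the next scheduled visit.** Let g be the gap between visits and s the number of days from the previous visit to the last dose, s = 1 to g. The form is dropped when g − s > 2, that is when s ≤ g − 3. It then covers s on-drug days. With s evenly spread over the dropped values, the mean is (1 + 2 + … + (g − 3))/(g − 3) = (g − 2)/2.

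| Interval | g | Stop days for which the form is dropped | On-drug days lost: mean | Maximum |
|---|---|---|---|---|
| Visit 2 to 3, Visit 3 to 4 | 7 | 4 of 7 | 2.5 | 4 |
| Visit 4 to 5 | 16 | 13 of 16 | 7 | 13 |
| Each monthly interval from Visit 5 | 30 | 27 of 30 | 14 | 27 |

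**Final form collected at a separate ET visit.** The on-drug share of the recall period is s/(s + delay). A delay of 0 to 2 days keeps the form; 3 or more drops it.

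| Delay (days) | s = 15 | s = 27 |
|---|---|---|
| 3 | 15/18 = 83% | 27/30 = 90% |
| 7 | 15/22 = 68% | 27/34 = 79% |
| 14 | 15/29 = 52% | 27/41 = 66% |

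In each of these cases the excluded form is more than half on drug. The share falls as the delay grows, and the fix must allow for that.

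**The other end of the window.** SAP 11 opens the range at Visit 2 but admits only post-baseline assessments, and its baseline is the last value before the first dose. Dosing starts the morning after Visit 2 (Protocol 6.2.3), so by that definition Visit 2 is baseline. SAP 11.5.1, however, compares Group A forms with the 'Baseline' version from the antecedent study, which would make Visit 2 post-baseline. The efficacy rule in SAP 10 starts at Visit 3 and avoids the problem.

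**The case against.** The strongest reply is that the events are not lost. Adverse events are exempt from the cut. Suicidal ideation and behavior form a special-interest category with its own summary and listing (SAP 11.1.1). Symptoms found during an assessment become adverse events if the investigator judges them clinically significant (Protocol 7.2.3.3). Positive C-SSRS responders are listed, and SAP 18.4 puts all assessments in the listings. This stands, and it confines the defect to the C-SSRS summaries. A reader might infer that suicidality before stopping would vanish from the report; the documents do not support that. The backups are still partial: the adverse event route depends on investigator judgment, and the suitability review that uses C-SSRS results is not scheduled at Visit 16/ET (Protocol 7.2.3.12).

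It can also be said that the overall summary in SAP 11.5.1 covers the whole study and so overrides SAP 11. The text does not say so, and on that reading the Group B screening form would be counted too.

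A reader might infer that positive Visit 2 forms will be counted as on-treatment. That is not settled: the visit range includes Visit 2, while the term post-baseline, with the SAP 11 baseline, excludes it. The numerical effect should be small in any case, because exclusion criterion 18 bars children with a history of suicide attempt or with past or current suicidal ideation.

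Finally, one might suppose that psychiatric withdrawals cluster in the lost interval. Nothing in the documents shows this, and the sponsor's stated ground for stopping was lack of efficacy in SHP465-309.

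**Conclusion.** The point holds as a conditional defect. SAP 11 applies a collection-date cut to a look-back instrument, and with no limit on the ET delay a final form taken 3 or more days after the last dose drops out of the C-SSRS summaries. Completers dosed up to Visit 16, and children whose ET visit falls within 2 days of the last dose, lose nothing; it would be wrong to read this as a loss of every child's last weeks on drug.

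Where it applies from Month 1 on, and the form waits for the next scheduled visit, the loss is at most 27 on-drug days per child. The mean of 14 rests on evenly spread stop days. In the first two weekly intervals it is at most 4 days, and between Visits 4 and 5 at most 13. How many children are affected, and whether any had a positive response only on such a form, cannot be known from the documents. Any error is toward undercounting. It should be corrected because the summary serves the primary objective and the change is small.

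**What to change.** In SAP 11 and 11.5.1:

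1. Classify C-SSRS 'Since Last Visit' forms by recall interval, not collection date. Count as on-treatment every form from Visit 3 onward whose recall interval overlaps dosing, including the first form after the last dose.
2. Where the event date is known, assign the event by date with the TEAE window (last dose plus 3 days). Where it is unknown and the form is more than 2 days after the last dose, include the form, flag it, report the delay, and give a sensitivity count without the flagged forms.
3. Start the post-baseline range at Visit 3, as SAP 10 does, and show Visit 2 and the Group B screening form as pre-treatment rows.
4. Reword the general cut to match the FoTA definition, and keep it at 2 days for point measurements (blood pressure, pulse, ECG).

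The cost is a paragraph of SAP text, a changed window flag for the C-SSRS and one extra count. The drawback is that some off-drug days enter the last interval, more when the delay is long; the flag, the reported delay and the sensitivity count make that visible.

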11.1 Adverse Events

Adverse events will be coded using Version 18.0 of Medical Dictionary for Regulatory Activities (MedDRA).

An AE (classified by preferred term) that occurs during the treatment period will be considered a TEAE if it has a start date on or after the first dose of investigational product or if it has a start date before the date of the first dose of investigational product, but increases in severity on or after the date of the first dose of investigational product, and no later than 3 days following the last dose of investigational product. If more than 1 AE with the same preferred term is reported before the date of the first dose of investigational product, then the AE with the greatest severity will be used as the benchmark for comparison to the AEs occurring during the treatment period under the preferred term.

An overall summary of the number of subjects with TEAEs will be presented, including the number and percentage of subjects with any TEAEs, serious TEAEs, TEAEs related to investigational product, TEAEs leading to drug withdrawal, TEAEs by maximum severity, and serious TEAEs Leading to death.

The number and percentage of subjects reporting TEAEs will be tabulated by system organ class (SOC) and preferred term; by SOC, preferred term, and severity; and by SOC, preferred term, and relationship to investigational product. If more than 1 AE occurs with the same preferred term for the same subject, then the subject will be counted only once for that preferred term using the most severe and most related occurrence for the summarization by severity and by relationship to investigational product.

The incidence of common ($\geq 2\%$ of subjects in any treatment group of the antecedent studies, rollover or direct enroll group, or overall population) will be summarized by preferred term, sorted in decreasing frequency in the overall population. The incidence of TEAEs, serious TEAEs, and TEAEs leading to withdrawal will be summarized by SOC and preferred term, sorted in decreasing frequency in the overall population.

For the Safety Set, listings will be presented for all AEs, TEAEs related to investigational product, TEAEs leading to drug withdrawal, and serious TEAEs.

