9. PRIOR AND CONCOMITANT MEDICATION

Version WHODRUG March 2017 of the WHO drug dictionary will be used to classify prior and concomitant medications by preferred term.

Prior medication is defined as any medication taken prior to the date of first dose of investigational product in this study.

Concomitant medication is defined as any medication with a start date prior to the date of the first dose of investigational product and continuing after the first dose of investigational product or with a start date between the dates of the first dose and last dose of investigational product, inclusive.

Any medication with a start date after the date of the last dose of investigational product (post-treatment) will not be considered a concomitant medication

Both prior and concomitant medication usage will be summarized separately by the number and percentage of subjects receiving each medication within each preferred term by treatment group of the antecedent studies, current treatment (SHP465) for each enrollment type, and overall for the Safety Set. Medications can be counted both as prior and concomitant medication. Multiple medication usage by a subject in the same category will be counted only once for the purpose of the summaries.

All prior, concomitant and post-treatment medications will be listed for the Safety Set.

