11.1.1 Adverse Events of Special Interest

Adverse events of special interest will include psychiatric events of interest (categorized as psychosis/mania, suicidal, aggression and other events) listed in Table 3. Adverse event terms of special interest will be searched across the TEAE data and summarized with the total exposure (in subject-days).

Table 3 Psychiatric Events

Category	Preferred Term/Verbatim term
Signs and/or symptoms of psychosis/mania	Hallucination (any type, including visual, auditory, tactile, mixed, etc.)
	Delusion (any type including somatic, persecutory, grandeur, reference)
	Schizophrenia (any type)
	Psychotic disorder
	Transient psychosis
	Acute psychosis
	Paranoia
	Childhood psychosis
	Schizophreniform disorder
	Schizoaffective disorder
	Catatonia
	Mania
	Hypomania
Suicidal ideation and behavior	Depression suicidal
	Gun shot wound
	Intentional self-injury
	Non-accidental overdose
	Overdose
	Self injurious behavior
	Self injurious ideation
	Self-mutilation
	Suicidal ideation
	Suicidal attempt
Completed suicide	
Aggression and violent behavior	Aggression
	Anger
	Hostility
	Homicidal ideation
	Sexual offense
	Murder
Imprisonment	

Table 3 Psychiatric Events

Category	Preferred Term/Verbatim term
Miscellaneous psychiatric events (include events with serious outcome only)	Abnormal behavior
	Agitation
	Amnesia
	Confusional state
	Depressed mood
	Depression
	Disorientation
	Emotional disorder
	Emotional distress
	Feeling abnormal
	Memory impairment
	Mood altered
	Mood swings
	Personality change
	Thinking abnormal
	Anxiety
	Fearfulness
	Phobia
	Panic attack
	Sleep disturbance
Tics	
Obsessive or compulsive behavior	
Trichotillomania	

A separate listing will be provided for psychiatric AEs of special interest.

Adverse events of clinical interest include insomnia (including AEs with preferred terms of ‘INSOMNIA’, ‘INITIAL INSOMNIA’, ‘MIDDLE INSOMNIA’ and ‘TERMINAL INSOMNIA’), weight decrease and decreased appetite. The preferred terms for these 3 AEs will be reviewed prior to database lock to determine which will be used to identify them.

For each of these 3 AEs (insomnia, weight decrease and decreased appetite), the following information will be presented:

- Number and percentage of subjects reporting the TEAE
- Number of TEAEs
- Summary of onset day of first TEAE: The onset day of first TEAE is calculated as (onset date of first TEAE-date of first dose) + 1 for subjects who experienced the TEAE

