- Summary of duration of TEAE while on study drug: The duration of each event is the number of days from the onset of the TEAE, while on study drug during SHP465 6.25mg, until the earlier of the end date of the TEAE or the date of last dosing + 3 days.

If the date of the last dose is missing, then the date of the last day on study will be used. TEAEs that either overlap in time, or are adjacent in time will be merged into one TEAE only for the purposes of calculating duration of event. If a subject has multiple TEAEs that are not overlapping or adjacent in time, then the durations will be averaged for that subject. Summary statistics are then based on the averaged subject durations. The calculated duration includes only the duration of TEAEs.

- Number and percentage of mild, moderate, and severe TEAEs: Overlapping TEAEs with different preferred terms are counted as multiple TEAEs.
- Summary of the number of TEAEs per subject: Overlapping TEAEs with different preferred terms are counted as multiple TEAEs.
- Number and percentage of TEAEs that:
 - Resolved while on study drug
 - Ongoing
 - Dose interrupted
 - Dose withdrawn
 - TEAEs leading to discontinuation
- Number of subjects who discontinued investigational product due to the event
- Also, for each of these 3 AEs (insomnia, weight decrease and decreased appetite), the following information will be presented by actual dose and month:
 - Number of subjects in the study
 - Number and percentage of subjects with the TEAE
 - Number of TEAEs
 - Number and percentage of subjects who discontinued due to the TEAE
 - Number and percentage of mild, moderate and severe TEAEs. If a subject has more than one TEAE in the same week, then the worst severity is counted.

Month 1 will include TEAEs reported to have started from Visit 2 (Baseline) through Visit 5 (Month 1); Month 2 will include TEAEs reported to have started after Visit 5 (Month 1) through Visit 6 (Month 2), etc.

In addition, for each subject, all occurrences of each of these 3 AEs will be listed separately by treatment group of the antecedent studies, subject number, start date and stop date. The information presented will include: subject, sex, age, race, ethnicity, preferred term/adverse event, start date, stop date, onset day, study visit, last dose date, duration/imputed duration of TEAE (days), SAE, severity, effect on dosing and treatment on AE.

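### Events that began on SHP465 in study 112 or the 309 active arm and persist at constant severity enter no TEAE summary; a separate count of events ongoing at entry would show them

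*SAP*

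**What the plan says.** SAP 11.1 has two routes to a TEAE. The event starts on or after the first dose, or it qualifies "if it has a start date before the date of the first dose of investigational product, but increases in severity on or after" that date, up to 3 days after the last dose. Protocol 9.9 gives the same rule in shorter form. Neither passage says which study's first dose is meant.

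SAP 11.1.1 builds on that definition. For psychiatric events it states that "Adverse event terms of special interest will be searched across the TEAE data". For insomnia, weight decrease and decreased appetite it plans incidence, onset, duration, severity and by-month summaries, all from TEAEs. On onset: "The onset day of first TEAE is calculated as (onset date of first TEAE-date of first dose) + 1". On duration: "The calculated duration includes only the duration of TEAEs".

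SAP 2.1 fixes five columns: Group A from 112 on SHP465, Group A from 309 on placebo, Group A from 309 on SHP465, Group B, and Total. The 112 and 309 SHP465 columns hold children who had already received 6.25 mg in the antecedent study. Under protocol 7.1.1.3 and 6.2.3, Visit 2 for Group A falls on the day of the last antecedent site visit and 308 dosing starts the next morning.

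**The concern.** Long-term tolerability is the primary objective, and protocol 1.2 names insomnia, decreased appetite and decreased weight among the effects seen with SHP465. A child whose insomnia began on SHP465 in study 309 and continues unchanged through 308 has the event on study drug, yet the TEAE tables show that child as free of it. A Group B child with the same insomnia, starting after the first 308 dose, is counted.

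The columns stand side by side, so a lower rate in a pre-exposed column could be taken for better long-term tolerability when part of it comes from where the count starts. Efficacy is treated differently: under SAP 10.2.1, ADHD-RS-5 change in Group A runs from the antecedent baseline, so it includes any benefit gained there, while harm that began there is left out of the TEAE counts.

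**Working it through.** There is no planned figure to reproduce: the study is descriptive, and no event rate or column size is given. The check is of definitions, followed by a simple scale.

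**1. Which first dose?** SAP 9 defines prior medication as taken "prior to the date of first dose of investigational product in this study". SAP 11 sets the safety baseline: "the last value collected before the first dose of investigational product in this study will be used as baseline for all analyses". In SAP 11.1.1 the Month 1 window opens at Visit 2 of 308. These three support the first 308 dose. SAP 2.1 points elsewhere, since it takes the antecedent baseline for Group A analyses, but it concerns baseline values and not adverse event dating. The first 308 dose is the best-supported reading.

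**2. Apply the rule.** Take a 309 active-arm child with mild insomnia that began on SHP465 and stays mild and continuous in 308.
- Start on or after the first 308 dose: no.
- Increase in severity on or after that dose: no.
- Result: 0 in the numerator for that event, 1 in the Safety Set denominator, and no entry in onset, duration or by-month rows.

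**3. Which events are lost?** Only continuous events at constant severity. Protocol 8.1.1 records a change in severity as a new event, so an event that eases from moderate to mild in 308 gets a new start date and can count. A recurrence after resolution also has a new start date and can count on the wording. Under SAP 18.6.1 and 18.7, a start date lacking only the day, in the month of first dose, is set to the first-dose date and also counts.

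**4. Which terms can carry over?** Insomnia, decreased appetite and weight decrease, if tolerable. From SAP Table 3, mainly non-serious aggression terms. Protocol 4.2 excludes children with a serious TEAE in an earlier SHP465 trial (item 1), psychosis or bipolar disorder (item 15), and past or current suicidal ideation (item 18). The remaining category is restricted by its own heading, "Miscellaneous psychiatric events (include events with serious outcome only".

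**5. Does another output supply the count?**

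| Output | What it shows | What it lacks |
|---|---|---|
| AE listings (SAP 11.1, 11.1.1) | Individual events with dates, if entered as 308 AEs | A percentage; 308 collection starts at 308 consent (protocol 8.1) |
| Medical-history listing (SAP 7.2) | Possibly conditions added at Visit 2 (protocol 7.2.3.1) | A count; SAP 7.2 describes Group A history only from antecedent screening |
| Weight change and the 7% flag (SAP 11.3) | Loss after 308 entry | Loss already incurred on drug, which lies inside the SAP 11 baseline |
| Weight and BMI percentile and z-score categories (SAP 11.3) | Status at each visit | Whether the loss began on drug |
| PSQ and CSHQ (SAP 11.5.2, 11.5.3) | Observed sleep scores by visit | Which problems began on drug |
| Appetite review (protocol 7.2.3.12) | Clinical check at visits | Any SAP summary outside adverse events |

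None gives the share of pre-exposed children with the event already present on drug.

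**6. Scale.** If k children in a column of n have such an event and are not otherwise counted for it, the shortfall is k/n. For Total, per child:
- Protocol 9.6, about 145 enrolled: 1/145 = 0.0069, or 0.7 percentage points.
- SAP 2.5, about 80 enrolled: 1/80 = 0.0125, or 1.25 percentage points.

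k is not in the documents and may be 0. The 309 placebo and Group B columns are unaffected, because events that predate 308 there did not begin on antecedent SHP465.

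**The case against.** The strongest reply is that nothing is wrong with the rule. A TEAE table measures new or worsened events in the study at hand, the SAP matches the protocol, and the anchor can be worked out from neighbouring sections. That stands: this is a case for one added count, and the definition should not change.

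Eligibility also thins out these events. Protocol 4.1 requires 112 rollovers to have had no clinically significant TEAE, and 309 rollovers none that would preclude further exposure. Protocol 4.2 further excludes conditions that could confound safety assessment, amphetamine intolerance, and weight at or below the 5th percentile. What remains is mostly mild or tolerable. The study is descriptive (SAP 2.6) and was stopped after 309 found this dose not efficacious at 6 to 12 years (SAP 1). These points lower the weight but do not supply the count.

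Three stronger readings are tempting and not supported:
- That every event which does not worsen is lost. Improving and recurring events can still count, as shown in step 3.
- That the shortfall can be put at several percentage points. The documents give neither the carried-over share nor the pre-exposed share of Total, and say nothing of antecedent treatment duration or the interval from last antecedent dose to Visit 2. Any such range would be assumption.
- That one child decides whether a term reaches the 2% table of common TEAEs. The cut is met if it is reached by 2% "of subjects in any treatment group of the antecedent studies, rollover or direct enroll group, or overall population". A term can therefore qualify through any column, including an unaffected one.

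**Conclusion.** The point holds as an inexpensive improvement of low to moderate weight. On the 308-dose reading, the Group A 112 SHP465, Group A 309 SHP465 and Total columns can read lower than the share of children with the event on drug, and the rule cannot push them above that share. In the by-age layout the combined Group A column and Total are affected. The supported size is per child only, as calculated above; the total effect is unknown and possibly nil. The conclusion rests on the first 308 dose being the anchor and on at least one event being continuous, constant in severity and reliably dated before entry. A reader might infer that a lower rate in a pre-exposed column conceals harm. The documents do not show that; they show only that the planned tables cannot distinguish no carry-over from uncounted carry-over.

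**What to change.** In SAP 11.1.1, for the Group A 112 SHP465 and Group A 309 SHP465 columns, add one row for each of insomnia, decreased appetite, weight decrease and aggression. Each row gives the number and percentage of subjects whose event began on SHP465 in the antecedent study and was ongoing at the first 308 dose, taken from antecedent adverse event records and Visit 2 history. Keep these rows apart from the TEAE counts, which stay as planned.

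Alongside, state in 11.1 and 11.1.1 that the first dose is the first SHP465-308 dose, and that onset day may be read as time from first study exposure to SHP465 only in the 309 placebo and Group B columns. These sentences are clarification only; the rows are the substance.

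The cost is four rows in two columns plus reconciling adverse event records and Visit 2 history from two antecedent studies, whose coding and collection rules are not visible here. The result may be small or zero, but a reported zero would answer the question.
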